7.5.1 Study Conduct

All protocol deviations will be listed and summarized.

7.5.2 Study Population

Frequency distributions or summary statistics of data pertaining to subject disposition, demographics, baseline characteristics, and medical history will be tabulated.

7.5.2.1 Subject Disposition

The disposition of subjects, including the number of subjects screened, the number of subjects randomized, the number of randomized subjects who received at least 1 dose of study drug, and the number of subjects who prematurely discontinue study drug will be tabulated. The number of subjects enrolled in the open-label extension study will also be tabulated.

7.5.2.2 Demographics and Baseline Characteristics

Demographic and baseline characteristics of subjects will be summarized descriptively by means and standard deviations for continuous variables, and frequency distribution for categorical variables. Summaries will be performed based on all randomized subjects (ie, ITT Population).

7.5.2.3 Medical History and Prior Medication

Medical history and prior medication information will be summarized.

7.5.3 Extent of Exposure

The extent of exposure to ataluren treatment is defined as the last dose date minus the first dose date + 1 day. The frequency will be presented according to the duration ranges (in days): ≤ 28 (≤ 4 weeks), 29 to 42 (4–6 weeks), 43 to 84 (6–12 weeks), 85 to 112 (12–16 weeks), 113 to 154 (16–22 weeks), 155 to 196 (22–28 weeks), 197 to 364 (28-52 weeks), 365 to 532 (52-76 weeks), 533 to 700 (76-100 weeks), 701 to 868 (100-124 weeks), and 869 to 896 (124-128 weeks). The number of subjects in each category as well as the mean duration will also be displayed.

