1.5 Study Design

[figure not shown]
Crossover designs are usually statistically efficient and thus require fewer subjects. Additionally, the influence of confounding covariates is reduced because each crossover subject serves as his or her own control. A 12-week treatment period with ataluren provides sufficient time to assess changes in the subject's seizure activity and QOL while still allowing appropriate monitoring of the subject. Due to the lack of effective alternative treatment, subjects and their parents/legal guardians will be motivated to participate in this study. Therefore, we expect a low dropout rate.

The study to be conducted is a Phase 2 interventional study which includes the following: Screening (Week -4 to Week 0/Day 1), Treatment Period 1 (Week 0/Day 1 to Week 12), Washout Period (Week 12 to Week 16), crossover to Treatment Period 2 (Week 16 to Week 28), and a Follow-up visit after 4 weeks. Subjects who complete this study may be eligible to enroll in a 96-week open-label extension study (Week 28 to Week 124). A Follow-up visit is to occur 4 weeks after the last dose of study drug for all subjects, regardless of whether a subject discontinues prematurely or completes the End-of-Study (EOS) visit and/or the open-label extension. For subjects who enroll in the extension study, Follow-up is scheduled to occur at Week 128. The opportunity to enroll in the extension study will be explained to subjects during the initial study informed consent by the site investigator; subjects enrolling in the extension study do not need to re-consent.

The treatment period in this study ends at Week 124 (Visit 11). However, for subjects that want to continue on study medication beyond Week 124, PTC Therapeutics will continue to supply drug. All subsequent visits will be standard of care and any blood work will be at the discretion of the investigator. A follow up visit for subjects who do not want to continue will be scheduled 4 weeks following the last dose. Access to study drug will continue until commercial availability of ataluren for this indication or until a positive risk-benefit assessment in this indication is not demonstrated whichever is first.

The study design is shown in Figure 2. The Schedule of Events is provided in Table 1.

Figure 2: Study Design

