1.5.1 Drug Administration Plan

Subjects will receive 12 weeks of ataluren or placebo during each treatment period. Treatment Period 1 will be followed by a 4-week Washout Period. Based on ataluren PK and pharmacodynamic data, the 4-week washout period is deemed an appropriate length of time to eliminate any ataluren drug effects. Following the Washout Period, subjects will crossover to receive the opposite treatment during Treatment Period 2 as follows:

- Subjects receiving ataluren during Treatment Period 1 will receive placebo during Treatment Period 2.
- Subjects receiving placebo during Treatment Period 1 will receive ataluren during Treatment Period 2.

Study drug will be administered 3 times per day (TID). The dose level to be administered is: 10 mg/kg in the morning, 10 mg/kg at midday, and 20 mg/kg in the evening.

Dosing will be based on the subject's body weight at Baseline. Weight will be assessed at every clinic visit. If the subject's body weight changes by $\geq 10\%$ from Baseline, the actual dose may be re-calculated.

The first dose of study drug will be administered in the clinic and the date and time of administration will be recorded. At the end of each Treatment Period, the last dose of study drug will be taken on the evening before the clinic visit (ie, the night before the Visit 4/Week 12 [end of Treatment Period 1] and the night before Visit 7/Week 28 [end of Treatment Period 2]).

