4.2 Treatment Regimen

Subjects will receive 90 days (12 weeks + 6 days) of masked ataluren or placebo during each treatment period. Each subject will start at a dose based on their weight in kilograms. The study drug is to be administered in a TID fashion of 10 mg/kg, 10 mg/kg and 20 mg/kg (morning, midday, and evening, respectively). The dose will be administered from 125, 250, and 1000 mg foil packets.

Dosing will be based on the subject's body weight at Baseline. Weight will be assessed at every clinic visit. If the subject's body weight changes by $\geq 10\%$ from Baseline, the actual dose maybe re-calculated.

The first dose of study drug will be administered in the clinic and the date and time of administration will be recorded. At the end of each Treatment Period, the last dose of study drug will be taken on the evening before the clinic visit (ie, the night before the Visit 4/Week 12 [end of Treatment Period 1] and the night before Visit 7/Week 28 [end of Treatment Period 2]).

Intervals for dosing should be ~6 hours (D1 hour) between morning and mid-day doses, ~6 hours (D1 hour) between mid-day and evening doses, and ~12 hours (D1 hour) between evening doses and the morning dose on the next day.

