b. During Treatment Period 2, subjects will crossover and begin receiving masked study drug opposite of what they received during Treatment Period 1 (ie, subjects previously receiving masked ataluren will now receive placebo and subjects previously receiving placebo will now receive ataluren).

01 Aug 2019

- c. The EOS visit (Week 28) will be completed for all subjects who complete or discontinue early from Treatment Period 1 and 2. Subjects who complete the EOS visit may continue in the open-label portion of the study at Week 28, otherwise a follow-up visit should be scheduled after 4 weeks.
- d. All subjects enrolling in the open-label extension study will receive ataluren 10, 10, 20 mg/kg 3 times per day for 96 weeks.
- e. The Follow-up visit is to occur 4 weeks after the last dose of study drug, regardless of whether the subject discontinues prematurely or completes the EOS visit and/or the open-label extension.
- f. Visit 2 is considered the Baseline Visit. Visit 2 must occur no sooner than 28 days and up to 42 days after Visit 1. All study and laboratory assessments must be completed prior to the first dose of study drug administration.
- g. If the subject begins but does not complete the open-label extension, complete EOT (Week 124).
- h. The first dose of study drug should be given in the clinic at Visit 2 (Baseline), Visit 5 (Week 16), and, if applicable, in the open-label extension at Visit 7 (Week 28).
- i. The last dose of study drug prior to Visit 4/Week 12 (Treatment Period 1) and Visit 7/Week 28 (EOS Visit) should be taken the night before, at home. No morning dose should be taken prior to the clinic visit.
- j. Serum HCG samples taken only for female subjects of childbearing potential
- k. Ataluren plasma PK will be assessed at 0 hr (pre-dose) at Visit 5/Week 16 and at 0 hr (pre-dose) and 2 hr post-dose at Visit 3/Week 6 and Visit 6/Week 22.
- l. AED plasma PK will be assessed at 0 hr (pre-dose of AED, including but not limited to valproate, clonazepam, lamotrigine, topiramate, and levetiracetam).

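### Section 7.5.3 measures ataluren exposure as one first-to-last-dose span, so washout and placebo time (112 days on schedule) counts as ataluren for ataluren-first subjects who enter the extension

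*Combined protocol and SAP*

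**What the plan says.** The exposure rule in Section 7.5.3 is a single span: "The extent of exposure to ataluren treatment is defined as the last dose date minus the first dose date + 1 day". Subjects are then placed in day ranges ending with "and 869 to 896 (124-128 weeks"), and "The number of subjects in each category as well as the mean duration will also be displayed".

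The design behind that rule is not one continuous course:

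- Section 1.5.1: "Subjects receiving ataluren during Treatment Period 1 will receive placebo during Treatment Period 2", after a 4-week washout. Placebo-first subjects do the reverse.
- Section 4.2: at the end of each masked period "the last dose of study drug will be taken on the evening before the clinic visit" (Visit 4/Week 12 and Visit 7/Week 28).
- Table 1, footnote d: "All subjects enrolling in the open-label extension study will receive ataluren 10, 10, 20 mg/kg 3 times per day for 96 weeks".
- Table 1, footnote h: the first dose is given in clinic at the start of each masked period and, where applicable, "in the open-label extension at Visit 7 (Week 28").
- Section 1.5: "for subjects that want to continue on study medication beyond Week 124, PTC Therapeutics will continue to supply drug".

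No section removes washout or placebo days from ataluren exposure, and none says whether a dose in Section 7.5.3 means an ataluren dose or any study-drug dose.

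**The concern.** A first-to-last-dose span equals time on drug only when the drug is taken throughout. Here an ataluren-first subject who continues into the extension takes ataluren to Week 12, nothing to Week 16, placebo to Week 28, and then ataluren again. The gap is a planned 16 weeks that includes the trial's own comparator, which is different from an incidental interruption. Counting it as ataluren contradicts the quantity being defined.

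What is at stake is the description of how much ataluren experience lies behind the safety data. Characterizing safety is a stated secondary objective in Section 2.1, and Section 7.1 still calls it the primary one. The displayed mean would be too long, some subjects would fall in too high a category, and two subjects with identical ataluren time could be reported differently because of their randomized sequence.

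**Working it through.** **The plan's own figures.** The upper limits of the duration ranges are study weeks times 7: weeks 4, 6, 12, 16, 22, 28, 52, 76, 100, 124 and 128 give 28, 42, 84, 112, 154, 196, 364, 532, 700, 868 and 896 days. All 11 match Section 7.5.3, so the ranges follow the study calendar, not ataluren time.

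**Inputs (study days, first dose on Day 1).** Visit 4 is Day 85, so the last Period 1 dose is on Day 84. Visit 5 is Day 113. Visit 7, with the first extension dose, is Day 197. Visit 11 is Day 869. Table 1 allows ±6 days per visit. I assume the last extension dose is also taken the evening before the visit; the documents state that rule only for Visits 4 and 7.

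**Days wrongly counted, ataluren-first subject in the extension.**

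Gap = first extension dose day − last Period 1 dose day − 1 = 197 − 84 − 1 = 112, which is 28 washout + 84 placebo days. With Visits 4 and 7 each moving by ±6 days, the gap is 100 to 124.

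| Last dose before | Formula | True, on schedule | Excess | True, gap 124 to 100 | Excess |
|---|---|---|---|---|---|
| Week 52 | 364 | 364 − 112 = 252 | 364/252 = +44% | 240 to 264 | +52% to +38% |
| Week 124 | 868 | 868 − 112 = 756 | 868/756 = +15% | 744 to 768 | +17% to +13% |

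**Placebo-first subject.** Ataluren runs without a break from Week 16: (52 − 16) × 7 = 252 days at Week 52 and (124 − 16) × 7 = 756 at Week 124. If a dose means an ataluren dose, the formula gives exactly these values. It is also right for subjects of either sequence who do not enter the extension (84 days).

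**If a dose means any study-drug dose.** Every subject who completes Week 28 is overstated by 112 days: 196 shown against 84 true without the extension, and 868 against 756 at Week 124 for both sequences.

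**Categories.** Comparing the range for a span *s* with that for *s* − 112, over *s* = 197 to 896, the category is too high for spans of 197–308, 365–476, 533–644, 701–812 and 869–896 days. It is unchanged at 364, 532, 700 and 868, including with gaps of 100 or 124. For a stop at Week 40, an ataluren-first subject is shown as 280 days (range 197–364) against 280 − 112 = 168 true. A placebo-first subject stopping then has (40 − 16) × 7 = 168 days and is shown as 168 (range 155–196). The documents give no distribution of stop times, so no probability of misclassification can be stated.

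**Top range.** Scheduled ataluren time is at most 84 + 672 = 756 days. With windows it is at most 90 + (874 − 191 + 1) = 774. Neither reaches 869. On ataluren time, the last range can be filled only by miscounted days or by drug supplied after Week 124.

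**Mean (a dose taken as an ataluren dose).** Excess = gap × share of subjects who are ataluren-first and enter the extension. It is 0 if none enter. Assuming that all 15 randomized subjects enter and 7 or 8 are ataluren-first, it is 7/15 × 112 = 52 to 8/15 × 112 = 60 days; with windows, 7/15 × 100 = 47 to 8/15 × 124 = 66. Extension numbers and sequence counts are not given. The total of 15 adds the 7 and 8 in Section 7.1, where both counts carry the same disorder label.

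**The case against.** The strongest reply is that little depends on this table. Adverse events are crude percentages of subjects (Section 7.6.1), compliance uses drug actually taken (Section 7.5.3.2), efficacy is analysed by treatment period (Section 7.7), and no test or decision rule uses exposure. An on-schedule completer stays in the right category. All of that stands and limits the consequence, but it does not make the rule correct: the mean is displayed too.

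Several narrower points also have some force:

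- *Pooling.* Section 7.5 summarizes within disorder group. With 3 or 4 of 7 and 4 of 8 subjects ataluren-first, all entering the extension (assumption), the excess is 3/7 × 112 = 48 to 4/7 × 112 = 64 days in one group and 4/8 × 112 = 56 in the other. The size is similar. Siblings share an allocation (Section 4.3), so an even split is not assured.
- *The 90-day figure.* Section 4.2 also gives 90 days of drug per masked period, which does not match the 84-day visit schedule and should be reconciled with it. On that figure the gap is 196 − 90 = 106 days and the maximum 90 + 672 = 762, both inside the windowed limits above.
- *Windows at later visits.* Keeping the right category at Weeks 52, 76, 100 and 124 holds on nominal days. A Visit 8 stop with last dose on Day 370 gives 370 (range 365–532) against 258 true (range 197–364).
- *The sequence contrast.* It depends on reading a dose as an ataluren dose. Under the other reading the contrast at Week 124 disappears, but only because both sequences are then overstated.

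**Conclusion.** The concern holds. Applied as written, Section 7.5.3 adds 112 days (100 to 124 with windows at Visits 4 and 7) of washout and placebo to the ataluren exposure of every ataluren-first subject who doses in the extension. This per-subject error does not depend on how many subjects enter. It is proportionally largest early in the extension: +44% at Week 52, falling to +15% at Week 124.

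The effect on the reported mean depends on unstated counts: none if no ataluren-first subject enters, and about 52 to 60 days under the all-enter assumption. The scope is narrow if a dose means an ataluren dose, and extends to everyone completing Week 28 if it means any study drug. The definition should be corrected, but the efficacy results and crude adverse-event percentages do not change.

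**What to change.** Define ataluren exposure as the sum, over each ataluren dosing interval (the masked ataluren period and, where entered, the extension), of last ataluren dose date − first ataluren dose date + 1, excluding washout and the placebo period. State that a dose here means an ataluren dose, and report placebo exposure by the same rule. Reset the duration ranges to ataluren time, with a scheduled maximum of 108 weeks (756 days) and an open-ended top range for subjects who stay on supplied drug after Week 124.

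The sum needs wording and programming only. It adds two dates for ataluren-first extension subjects: the last masked ataluren dose, planned for the evening before Visit 4, and the first extension dose, planned in clinic at Visit 7. Their reported exposure becomes smaller. Counting drug taken after Week 124 has a further cost: Table 1 schedules no drug return or compliance review after Visit 11, so those dose dates would have to be collected. Otherwise the plan should say that exposure is cut off at Week 124.

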7.5.3.1 Discontinuation of Study Therapy

The ITT Population will be used to summarize discontinuation from study drug as indicated in Section 7 as well as the reason for the premature termination of study drug. The proportion of subjects who discontinue study drug will be summarized using point estimates and 95% CI.

7.5.3.2 Treatment Compliance

Study drug compliance will be assessed by analysis of unused study drug reported. This information will be used to describe and summarize compliance by disorder group and treatment group. Compliance will be assessed in terms of the percentage of drug actually taken relative to the amount that should have been taken during the study.

7.6 Safety Analyses

All safety presentations will be based on the ITT Population and will be based only on data included in the analysis period of interest. Listings of all AEs will also be based on all available data at the scheduled analysis time point. Adverse event and SAE summaries will also be presented for the following periods:

- Up to the end of Visit 4 (Week 12)
- Up to the end of Visit 7 (Week 28, EOS Visit)
- Between the start of Week 17 and the end of Week 28.
- Up to the end of the open-label extension (Week 124, if applicable)
- Between the start of Week 29 and the end of Week 124 (if applicable).

Additional frequency tables summarizing the occurrence of AEs and SAEs after the end of the analysis period of interest will also be provided. All AEs and SAEs will be summarized by treatment group. Marked laboratory abnormalities will also be descriptively summarized. No statistical tests will be performed for AEs or laboratory marked abnormalities.

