7 STATISTICS

7.1 Sample Size Determination

The original study was not powered for statistical testing since the primary objective is to characterize the safety profile of ataluren in subjects with CDKL5 or Dravet syndrome resulting from a nonsense mutation. Eighteen subjects (10 with CDKL5 syndrome and 8 with Dravet syndrome) was planned to be included in this study. At the time of protocol amendment, 7 subjects Dravet syndrome have been randomized and 8 subjects with Dravet syndrome have been randomized. Enrolment has been stopped. The number of subjects randomized will provide an initial assessment on the efficacy for subjects with CDKL5 syndrome and with Dravet syndrome.

The number of subjects enrolled in the open-label extension study will be determined by the number of subjects who complete the initial study and remain eligible to participate in the extension study.

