7.2 Randomization

Eighteen subjects (10 with CDKL5 syndrome and 8 with Dravet syndrome) will be enrolled. Within each disorder group, subjects will be randomized in a 1:1 ratio to 1 of 2 possible treatment assignments during Treatment Period 1:

- Placebo
- Ataluren (10, 10, 20 mg/kg/day)

After the completion of Treatment Period 1 and a 4-week Washout Period, subjects will crossover and begin receiving masked study drug opposite of what they received during Treatment Period 1 (ie, subjects previously receiving masked ataluren will now receive placebo and subjects previously receiving placebo will now receive ataluren).

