7.3 Populations for Analyses

Intent-to-Treat (ITT) Population - The ITT Population will contain all randomized subjects.

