7.6.1 Adverse Events

Summary information (the number and percent of subjects by treatment) will be tabulated for:

- TEAEs, including clinical and laboratory AEs

- Treatment-related AEs
- TEAEs by severity
- Treatment-related AEs by severity
- SAEs
- AEs leading to discontinuation

Summaries will be presented by treatment groups and categorized by System Organ Class and Preferred Term. The frequencies of AEs displayed will be the crude rates that represent the number of subjects experiencing AEs divided by the total number of subjects.

It should be noted that all laboratory data sent to and analyzed by the NYU laboratory will be reported to the investigator. However, only those laboratory abnormalities meeting the protocol-defined criteria of an AE (ie, those that require clinical intervention or further investigation beyond ordering a repeat [confirmatory] test) should be reported as AEs in the appropriate CRF, whether they were analyzed by the NYU laboratory or another laboratory.

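### Sections 7.3, 7.6 and 7.6.1 do not limit a treatment's AE denominator, overall or in a given analysis window, to the subjects exposed to it

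*Combined protocol and SAP*

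**What the plan says.** Section 7.3 defines one analysis population: "The ITT Population will contain all randomized subjects". It sets no dosing condition and names no safety or as-treated set.

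Section 7.6 applies that population throughout: "All safety presentations will be based on the ITT Population". It asks for AE and SAE summaries by treatment group in five windows: to Week 12, to Week 28, Weeks 17 to 28, to Week 124, and Weeks 29 to 124. It limits the tables to data from the period concerned, and it plans no statistical tests on AEs.

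Section 7.6.1 describes the tables ("Summary information (the number and percent of subjects by treatment) will be tabulated for" a list of AE categories) and the rate: "The frequencies of AEs displayed will be the crude rates that represent the number of subjects experiencing AEs divided by the total number of subjects".

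On design, Section 7.2 says that after Period 1 and the washout "subjects will crossover and begin receiving masked study drug opposite of what they received during Treatment Period 1". Section 7.1 makes extension numbers depend on who completes and remains eligible. Sections 3.6.1, 4.4 and 8.6 foresee exits for toxicity, seizure worsening, poor compliance and unmasking. Section 7.5.2.1 counts randomized and dosed subjects separately, but only for disposition.

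**The concern.** In a parallel-group trial, using all randomized subjects as the safety denominator usually does little harm, because nearly everyone randomized to an arm starts that arm's treatment. In a crossover, a subject reaches the second treatment only by staying until Week 16. Someone who leaves earlier has no opportunity for an AE on the second treatment. If that subject stays in its denominator, the table treats no exposure as exposure without an event.

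The extension has the same problem without any dropout. A child who completes Week 28 and does not continue has no extension exposure, yet no denominator other than ITT is given for Weeks 29 to 124.

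Characterizing safety is a stated objective (Section 2.1), and Section 7.1 even calls it primary. With no AE tests planned, the crude percentages are the main comparative safety summary. Exits for toxicity or seizure worsening are unlikely to be independent of treatment, so the dilution need not be equal in the two columns.

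**Working it through.** The plan states no AE rate or dropout rate, so there is no figure of its own to reproduce. The check is how far the literal denominator moves a rate.

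**Inputs**
- Planned N: 10 + 8 = 18 (Section 7.1).
- Randomized N at the amendment, with enrolment stopped: 7 + 8 = 15 (Section 7.1). Both groups are labelled Dravet there; I assume they are the two disorder groups and use N = 15.
- Allocation to sequence: 1:1 within disorder group (Section 7.2).
- Number never exposed to a given treatment, d: not given. Section 1.5 expects few dropouts. Assumed range 0 to 3.
- Event counts and exposed rates below: assumptions for illustration.

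**Formula.** With x subjects having an AE on a treatment, the literal rate is x/N and the rate among the exposed is x/(N - d). So literal rate = exposed rate × (N - d)/N, and the relative understatement is d/N.

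**Both periods pooled (window to Week 28), N = 15**

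| d | (15 - d)/15 | Relative understatement | Shown if exposed rate is 40% | 5 subjects with an AE: literal vs exposed |
|---|---|---|---|---|
| 0 | 1.000 | 0% | 40.0% | 33.3% vs 33.3% |
| 1 | 0.933 | 6.7% | 37.3% | 33.3% vs 35.7% |
| 2 | 0.867 | 13.3% | 34.7% | 33.3% vs 38.5% |
| 3 | 0.800 | 20.0% | 32.0% | 33.3% vs 41.7% |

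**Within a disorder group.** Section 7.5 calls for summaries by disorder group. With 3 subjects having an AE and one never exposed:
- group of 7: 3/7 = 42.9% against 3/6 = 50.0%;
- group of 8: 3/8 = 37.5% against 3/7 = 42.9%.

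Two leavers from one sequence in the group of 7 would give 3/5 = 60.0%. That sequence would hold only about 3 or 4 children, so this means losing half or more of it. I treat it as an extreme case.

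**Contrast between treatments.** Suppose the exposed rate is 40% on both treatments and N = 15.
- Two placebo-first subjects leave before Week 16: ataluren 40 × 13/15 = 34.7%, placebo 40.0%, difference -5.3 points.
- Two ataluren-first subjects leave: ataluren 40.0%, placebo 34.7%, difference +5.3 points.
- One leaves from each sequence: 40 × 14/15 = 37.3% on both, difference 0.

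**Windows**
- Week 12 table: with 1:1 allocation, about half of those randomized have taken only placebo. Putting all 15 under the ataluren column would roughly halve its rate with no dropout at all.
- Weeks 29 to 124: d is the number who did not enter the extension, and the same formula applies.
- Washout (Weeks 12 to 16): an AE arising here falls inside the cumulative windows but in neither single-period window. No text says which treatment column takes it.

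**The case against.** The best defence is that Section 7.6.1 speaks of subjects by treatment, so the total could mean the total in that treatment's column for that period. The Week 12 table supports this, since the literal rule gives an absurd denominator there. A sensible programmer might well use the exposed N. This is plausible, but it is written nowhere, and it departs from the instruction to base every safety presentation on all randomized subjects. Limiting tables to data from the period of interest restricts which events count; it sets no denominator. That the literal rule fails on the plan's first listed window is a reason to correct the rule.

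Other parts of the defence stand:
- With no early leavers and everyone dosed, no percentage in the table to Week 28 changes. The first dose is given in clinic (Section 1.5.1), so never-dosed subjects should be rare.
- Counts are shown with percentages, all AEs are listed, and disposition, exposure and discontinuations are reported. In a trial this small, a reader could largely recover the exposed N.
- No AE test or powered comparison depends on these rates.

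A reader might also infer that using ITT classifies AEs by assigned treatment. The text does not support that: Section 7.3 says only who is included, and Sections 7.6 and 7.6.1 do not say how subjects are placed in columns.

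**Conclusion.** The point holds as a defect in the stated denominator. Together, the three sections put all safety tables on everyone randomized and define a crude by-treatment rate, with no limit to those exposed.

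The size is conditional. With 15 randomized and 0 to 3 assumed never exposed to a treatment, the relative understatement in the table to Week 28 runs from 0% to 20%, or 0 to 8 points at an exposed rate of 40%. One unexposed subject matters more within a disorder group of 7 or 8. The leaver counts, event counts and exposed rates are assumptions, because the documents supply none.

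It would be tempting to conclude that AE rates are understated as a matter of course, or that the rule favours ataluren. Neither follows. Understatement arises only if someone counted is unexposed, and only for the treatment or window not received. Placebo-first leavers lower ataluren's rate and ataluren-first leavers lower placebo's, so the contrast can shift either way or cancel.

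**What to change.** In Sections 7.6 and 7.6.1:

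1. Set each treatment column's N, in each analysis window, to the subjects who took one or more doses of that treatment in that window.
2. Classify subjects and events by treatment actually received.
3. Print N at the head of every column.
4. State which column takes AEs arising in the washout (Weeks 12 to 16), for example the last treatment taken.

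A general safety population in Section 7.3 (anyone dosed with study drug) may be added, but it is not enough alone. A child who leaves during Period 1 has been dosed and would stay in it, and so could still be counted under the treatment never taken.

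The cost is a few sentences in Section 7 and no new data. Some percentages become slightly higher. If everyone is exposed to both treatments, the table to Week 28 keeps the same denominators.

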8.2 Adverse Event Reporting Period

The study period during which AEs must be reported is defined as the period from the initiation of any study procedures (ie, after informed consent is given) to the end of the study drug follow-up. For this study, the study drug follow-up is defined as 4 weeks following the final administration of study drug.

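### In Section 7.6 the Period 2 and open-label AE windows follow calendar weeks while dosing can start up to 6 days either side, and no rule says which treatment a washout-onset event counts under

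*Combined protocol and SAP*

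**What the plan says.** Section 7.6 of the combined protocol and SAP lists five periods for AE and SAE summaries:

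- "Up to the end of Visit 4 (Week 12"), which ends at a visit.
- "Up to the end of Visit 7 (Week 28, EOS Visit"), cumulative, which also ends at a visit.
- "Between the start of Week 17 and the end of Week 28", set purely by calendar week.
- Up to the end of the open-label extension, cumulative.
- "Between the start of Week 29 and the end of Week 124 (if applicable"), set purely by calendar week.

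The same section adds: "Additional frequency tables summarizing the occurrence of AEs and SAEs after the end of the analysis period of interest will also be provided". It also plans listings of all AEs. On attribution it says "All AEs and SAEs will be summarized by treatment group", and Section 7.6.1 calls for numbers and percentages of subjects by treatment, starting with "TEAEs, including clinical and laboratory AEs". The supplied text gives no treatment-emergent window.

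On timing, Section 1.5 puts the washout between Weeks 12 and 16. Table 1 allows each visit after screening 6 days either way. Its footnotes place the first dose of Period 2 at Visit 5 and the first open-label dose at Visit 7, both in the clinic. Section 1.5.1 has the date and time of the first dose recorded.

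**The concern.** Two of the five windows are tied to the calendar, but the treatment they are meant to describe starts at a visit that can move. When the visit moves, the window no longer matches the drug the subject is taking.

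Separately, this is a crossover in which every completer takes both treatments (Section 7.2), so a by-treatment AE table needs a rule for each interval. None is given for the washout. The cumulative window to Visit 7 contains the washout but pools both treatments within each subject. The after-period tables following Visit 4 would contain the washout together with the opposite treatment.

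The stake is the tolerability comparison in a small study. Dosing starts without titration (Synopsis), so the first days on drug are of particular interest. Section 8.1.2 counts withdrawal reactions among reportable AEs, and after Period 1 these would arise in the washout. Section 7.1 reports 7 and 8 subjects randomized in the two disorder groups. Moving one subject changes a crude rate by 1/15 = 6.7 percentage points overall, or by 1/8 = 12.5 to 1/7 = 14.3 points if everyone in a disorder group is the denominator.

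**Working it through.** The plan states no figure to reproduce, so the check is day arithmetic.

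**Convention.** Day 1 is the Week 0 visit. Week *w* covers Days 7(*w* − 1) + 1 to 7*w*. The nominal Week-*w* visit falls on Day 7*w* + 1. This matches the exposure bands in Section 7.5.3, whose upper limits (28, 42, 84, 112, 154, 196, 364, 532, 700, 868, 896) are all 7 × the stated week. Section 7.6 does not define its weeks, so using the same convention there is an assumption.

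**Window limits.**

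- Start of Week 17: 7 × 16 + 1 = Day 113.
- End of Week 28: 7 × 28 = Day 196.
- Start of Week 29: 7 × 28 + 1 = Day 197.
- End of Week 124: 7 × 124 = Day 868.

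**Visits moved by 6 days from the nominal day (Table 1).**

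| Visit | Shift | Day | Effect |
|---|---|---|---|
| 5 | −6 | 107 | 113 − 107 = 6 on-drug days fall before the Period 2 window |
| 5 | 0 | 113 | none |
| 5 | +6 | 119 | 119 − 113 = 6 washout days fall inside the Period 2 window |
| 7 | −6 | 191 | 197 − 191 = 6 open-label days fall inside the Period 2 window |
| 7 | 0 | 197 | none |
| 7 | +6 | 203 | last masked dose on Day 202; 202 − 196 = 6 masked days fall in the open-label window |

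Six days out of 12 × 7 = 84 is 7.1% of a treatment period.

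**Which treatment is affected at Visit 7.** An ataluren-first subject takes placebo in Period 2. An early Visit 7 therefore puts open-label ataluren days in that subject's placebo window, and a late one puts placebo days in the open-label ataluren window. For a placebo-first subject the drug is ataluren on both sides, so only the phase is wrong.

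**Washout.** Weeks 13 to 16 are Days 85 to 112, which is 28 days, or 28/196 = 14.3% of the nominal masked phase. Day 85 is itself the Visit 4 day. If that whole day counts in the first window, 112 − 85 = 27 days lie in neither period-specific window. With Visit 4 on Day 79 or Day 91, the figure is 33 or 21. All of these days lie inside the cumulative window to Visit 7.

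**Sensitivity to the meaning of Week 17.** If it means the nominal Week 17 visit day, 7 × 17 + 1 = Day 120, then 120 − 113 = 7 on-drug days are missed even at nominal timing. The range is 120 − 119 = 1 to 120 − 107 = 13.

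**The case against.** The strongest reply is that nothing is lost. Washout events sit in the cumulative window, in the after-period tables and in the listings. The five periods are introduced as additional summaries, and the by-treatment tables in Section 7.6.1 name no calendar window. Six days is the edge of the visit window, there are no AE tests, and about 15 subjects can be reviewed individually. The half-life is 2 to 6 hours (Section 1.2.1), and Section 1.5.1 judges four weeks enough to clear drug effects.

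Much of that stands, and it rules out several stronger readings that a reader might infer:

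- *All the windows are calendar weeks.* Only two of five are; the windows ending at Visits 4 and 7 move with the subject.
- *Washout events belong to no treatment or disappear from reporting.* The plan is silent on attribution, and the events are reported elsewhere.
- *First-dose events in Period 2 are routinely lost, or are counted under the other treatment.* On the Section 7.5.3 convention none is lost at nominal timing. If Visit 5 is early they miss the Period 2 window, but they cannot fall in the Period 1 window, which closed at Visit 4.
- *Section 8.2 already ties the washout to the Period 1 drug, because "the study drug follow-up is defined as 4 weeks following the final administration of study drug".* That sets how long AEs are reported after the final dose. It is not an attribution rule after Period 1.

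The reply does not supply the missing rule. The other outputs report washout events, but none says which treatment they count under. The tables in 7.6.1 need the same rule. The boundary error also follows directly from the windows as written.

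**Conclusion.** The point holds, with limited size. The two calendar windows can be out of step with dosing by up to 6 days at Visit 5 and at Visit 7. Events are then left out of the Period 2 window or wrongly included in it. The wrong-treatment case arises at Visit 7 in ataluren-first subjects. The washout, nominally 28 days, has neither a period-specific window nor an attribution rule, so the by-treatment tables are not fully specified.

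This rests on two assumptions: that Section 7.6 counts weeks as Section 7.5.3 does, and that the 6 days are measured from the nominal visit day. The figures are days at risk of misplacement, not expected numbers of events; the documents give no AE rate from which to estimate those. The 6-day figures are maxima. Because the AE summaries are descriptive, no type I error or power is involved. The change is worth making because it corrects a stated rule at almost no cost.

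**What to change.** In Section 7.6, replace the calendar windows with windows built from each subject's dose dates:

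1. Each period runs from its own first dose to the day before the first dose of the next period or, if there is none, to the end of follow-up.
2. Within a period, events with onset on treatment are shown under the current treatment.
3. Events with onset in the washout are shown as a separate row by preceding treatment.
4. State that the by-treatment and TEAE tables in Section 7.6.1 use these windows.

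Do not cap attribution at 28 days after the last dose, because that leaves days unassigned when the washout runs long. With Visit 4 six days early, the last dose is on Day 78 and the cap ends on Day 78 + 28 = Day 106. With Visit 5 six days late, on Day 119, Days 107 to 118 (12 days) would have no category.

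This removes the 6-day error at Visits 5 and 7. Starting Period 1 at its first dose also keeps pre-dose events out of the first window, which now has no stated start although AEs are collected from consent (Section 6.1.1). The cost is one rule and some table programming. First-dose dates are recorded (Section 1.5.1), and the exposure calculation in Section 7.5.3 already needs first and last dose dates, so no new data are required.
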